5.3 ALTERNATIVE TO PARTICIPATION

Subject participation is voluntary and should the subject choose to not participate in the study, they will be treated as per the standard of care.

6 OBJECTIVES

The primary objective of this study is to evaluate if pre-operative QST can identify if patients will have high pain intensity peri-operatively and at 6 months post-operatively. We will evaluate the intensity and chronicity of pain and the function of the descending inhibitory system through a short QST procedure before surgery and six months after surgery. In addition, we will evaluate the patient's physical and emotional functioning, and explore the potential biological underlying mechanisms at the same time points.

The secondary objective of this study is to determine if the peri-operative use of an alpha-2 adrenergic receptor agonist enhances the efficacy of the descending inhibitory system of patients with sub-optimal CPM efficacy before surgery by decreasing pain after surgery. Consequently, this pharmacological intervention may also reduce the incidence of acute and chronic pain after surgery. We will evaluate the pain intensity and the function of the descending inhibitory system through a short QST procedure six weeks after surgery and six months after surgery in patients receiving Clonidine or placebo during the perioperative period. We will also evaluate the patient's physical and emotional functioning, and explore the potential biological underlying mechanisms at the same time points.

We will also evaluate the potential biomechanical alterations in 3D related to pain in children reporting presence of back pain pre and post spine surgery.

Our hypothesis is that patients undergoing spine surgery with poor inhibitory pain response will have less pain in the immediate and long-term period when treated prophylactically with Clonidine in the perioperative period.

7 SUBJECT SELECTION

This study aims to recruit 150 female patients, with approximately 75 per group. The scientific rational to exclude male patients is straight forward. Knowing that gender can influence the quantitative sensory testing – knowing that gender can also affect pharmacokinetics, we felt prudent to minimize our variables to ensure our N will be able to show the expected outcome. If and once our hypothesis has been shown, then the protocol will be amended to include males to see if clonidine also improves acute chronic pain management.

7.1 INCLUSION CRITERIA

- Females* aged between 10 and 21 years old
- Scheduled to undergo anterior or posterior spinal fusion surgery for AIS with instrumentation
- Ability to adequately understand and respond to outcome measures
- No previous major orthopedic surgery
- Any ethnic background

*Inclusion of only females is due to inherent gender differences of the parasympathetic activity responsible for the endogenous inhibitory pain response [60].

7.2 EXCLUSION CRITERIA

- Children with history of allergies to Clonidine or its excipients in either injection or tablet formulation (see respective monograph)
- Children with history of galactose intolerance
- Children with history of myocardial disease, arrhythmias, cerebrovascular disease, Raynaud's/Thromboangiitis obliterans or chronic renal failure diagnosed based on history and physical
- Children taking antihypertensive agents (diuretics, vasodilators, beta-blockers, ace-inhibitors)
- History of depression
- Inability of the child to speak English or French
- Diagnosed with developmental delay that would interfere with understanding questions being asked (autism, mental retardation)
- Children with major chronic medical conditions (ASA status III or higher)
- Pregnancy excluded by an in hospital testing the night before surgery

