11.2.4 QST THERMAL FAMILIARIZATION PRE-TEST	32
12 PAIN ASSESSMENT QUESTIONNAIRES	34
12.1 In-Hospital Additional Measures:.....	35
12.1 STUDY PLAN TABLE	35
13. SUBJECT SAFETY	36
13.1 SAFETY AND TOXICITY ASSESSMENT	36
13.2 ADVERSE EVENT AND ADVERSE DRUG REACTION (adr).....	36
13.3 SERIOUS ADVERSE EVENT OR ADVERSE DRUG REACTION	37
13.4 ANTICIPATED ADVERSE DRUG REACTIONS.....	37
13.5 SERIOUS ADVERSE EVENT AND ADVERSE DRUG REACTION REPORTING	39
13.6 NOTIFYING HEALTH CANADA	39
13.7 UNBLINDING PROCEDURE	40
14 DATA HANDLING AND RECORD KEEPING	41
14.1 CONFIDENTIALITY AND SECURITY.....	41
14.2 QUALITY CONTROL AND QUALITY ASSURANCE.....	41
14.3 DATA STORAGE.....	41
14.4 CONFIDENTIALITY AND SECURITY.....	41
14.5 SOURCE DOCUMENTATION.....	42
14.6 RECORD RETENTION	43
15 QUALITY CONTROL AND QUALITY ASSURANCE.....	43
15.1 DATA SAFETY MONITORING BOARD (DSMB)	43
15.2 STUDY MONITORING PLAN	43

16 STATISTICAL CONSIDERATIONS	44
16.1 PRIMARY STUDY ENDPOINTS.....	44
16.2 SECONDARY ENDPOINTS	44
16.3 SAMPLE SIZE DETERMINATION AND POWER / ACCRUAL RATE	44
16.4 STATISTICAL METHODS.....	44
16.5 STRATIFICATION FACTORS.....	45
17 FINANCE.....	45
18 REFERENCES	45

Study Summary

Title	Sensorial and physiological mechanism-based assessments of perioperative pain
Short Title	RCT
Methodology	Randomized-controlled double-blind study
Study Duration	5 years
Study Site(s)	Shriners Hospital for Children Canada
Objectives	The overall goal of this proposal is to determine if quantitative sensory testing (QST) assessing pain modulation can be used as a clinical tool to optimize perioperative pain management. The central hypothesis is that the identification of patient's sensory pain profile allows personalizing therapeutic approaches to improve individualized pain management and thus prevents pain chronicity.
Number of Subjects	150 (approximately 75 for each arm)
Diagnosis and Main Inclusion Criteria	Female patients between 10 and 21 years old with a diagnosis of Adolescent Idiopathic Scoliosis (AIS) and no concomitant diseases, who are scheduled for scoliosis surgery at the Shriners Hospital, will be invited to participate in the study.
Study Product, Dose, Route, Regimen	Arm 1 - Intrathecal Clonidine after to surgery & PO Clonidine for 5 days post-op
Duration of administration	Day of surgery and 5 days post-operatively.
Reference therapy	Arm 2 - Intrathecal Morphine after to surgery & PO Placebo for 5 days post-op

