Alpha-2 adrenoceptor agonists currently represent the most versatile and well-tolerated adjunct for the neuroaxial blockade in children. Preservative-free morphine may be indicated in certain situations, but the risk for respiratory depression and other disturbing side-effects must be taken into account [50].

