9.2.2 PLACEBO-RANDOMIZED GROUP

Both the optimal and sub-optimal groups who were randomized to the placebo group will receive intrathecal spinal morphine (5 mcg / kg) at the end of the spinal procedure in the operating room.

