10 STUDY AGENT INFORMATION

QST results will show that subjects either have an optimal or a sub-optimal response. The subjects who fall into the optimal category will be randomized to either Clonidine or placebo and the subjects who fall into the sub-optimal category will also be randomized into either Clonidine or placebo. The hospital pharmacy will do 1:1 randomization using online software.

Randomization and blinding of the medications and placebo will be performed by the hospital pharmacy. The pharmacy will be sent the list of patients participating in the study. They will maintain the trial treatment randomization codes, and procedures for breaking codes will be also carried out by the pharmacy.

For each study patient, the physician will supply the pharmacy with a prescription ordering medication for the Clonidine arm OR the placebo arm according to what the patient is randomized to. The pharmacy will prepare the appropriate medication kits, according to the randomization assignment, either containing vials of Clonidine or intrathecal morphine. For the day of surgery, the pharmacy will prepare a blinded kit containing the medication, preparation materials and instructions. Either the evening before, or the morning of the surgery, the research assistant will go to the pharmacy and pick up the blinded study medication kit and deliver it to the OR. The respiratory therapist will prepare the medication contained in the kit in the operation room just prior to surgery and then give it to the anesthesiologist who will administer it to the patient.

The 5 days of post-operative medication, either Clonidine or placebo, according to patient's randomization prescription, will be dispensed daily from the hospital's pharmacy, along with their regular routine medications.

As per Standard of care, concomitant therapy will be provided for pain, anti-nausea and for any other reasons that may occur. These therapies will be given in addition to the study medications.

All medications given to the patient will be noted in the patient's medical chart by the nurse. The patient's medical chart will then be verified daily by a research assistant for study drug compliance. In the event of non-compliance, a Note File will be added to the patient's study file listing the reasons why, and the action taken and filed in the patient's study file. Providing patients wish to remain in the study, they will not be discontinued from the study for non-compliant medication intake.

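### The drug-allergy exclusion covers clonidine only, although half the patients are randomised to intrathecal morphine, so a patient with a known morphine allergy is eligible as written

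*Combined protocol and SAP*

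**What the plan says.** **Eligibility.** Section 7.2 excludes "Children with history of allergies to Clonidine or its excipients in either injection or tablet formulation (see respective monograph". The only other intolerance listed is "Children with history of galactose intolerance", which does not bear on morphine. Neither 7.1 nor 7.2 mentions allergy or intolerance to morphine or to opioids generally. The ASA III criterion concerns major chronic disease, not allergy.

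**Treatment.** The Study Summary defines the comparator as "Arm 2 - Intrathecal Morphine after to surgery & PO Placebo for 5 days post-op". Section 9.2.2 repeats that patients randomised to placebo, in both the optimal and sub-optimal CPM groups, "will receive intrathecal spinal morphine (5 mcg / kg) at the end of the spinal procedure in the operating room". Section 10 describes study kits "either containing vials of Clonidine or intrathecal morphine", and states: "The hospital pharmacy will do 1:1 randomization using online software". On numbers, section 7 says: "This study aims to recruit 150 female patients, with approximately 75 per group".

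**Blinding and safeguards.** Section 10 calls the day-of-surgery kit blinded, and section 8.1 keeps clinicians blinded unless unblinding is required. Section 13.7 gives the unblinding procedure, and each route in it starts from a side effect or event. Section 9.1 includes a medical history interview but states no allergy item and no eligibility consequence. Section 9.5.2 lets participation end at the physician's discretion. The monitoring checklist in 15.2 lists eligibility items to verify; drug allergy is not among them, whether to clonidine or to morphine.

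**The concern.** A patient should enter a two-arm randomised trial only if either allocated agent is acceptable for her. Section 7.2 accepts that principle, because it makes allergy to a study agent a question of eligibility. It then applies it to one of the two active intrathecal agents.

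The likely cause is the label. Calling the comparator arm placebo is accurate for the oral tablets but not for the intrathecal dose. The same one-sidedness appears elsewhere: the risks in 5.2 cover QST and clonidine, and the anticipated reactions in 13.4 come from the clonidine monographs only.

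Two things are at stake. One is a foreseeable safety gap in a young population. The other is trial conduct. If the allergy is recognised only after randomisation, the trial has a randomised patient who either does not receive her allocated agent or has her blind broken. Screening before randomisation avoids both.

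**Working it through.** The main check is a reading of the text; the arithmetic only sizes it.

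**Step 1: follow a hypothetical patient through the plan.** She meets every criterion in 7.1 and has a known morphine allergy.

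- *7.2:* she is not allergic to clonidine or its excipients and has no galactose intolerance. No other exclusion refers to her allergy, so she is eligible.
- *8.1:* all consecutive patients who meet the criteria are to be invited, so she is approached.
- *9.1 and the Study Plan Table:* she is randomised after the baseline QST results, before admission for surgery.
- *Section 10:* the pharmacy prepares a kit according to her allocation. It is collected the evening before or the morning of surgery. No allergy check before release is described.
- *13.7:* no side effect or event has yet occurred, so the written unblinding procedure is not triggered.

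No written step stops her between screening and dosing.

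**Step 2: chance of allocation to morphine.** With 1:1 allocation this is 1/2 = 50% for each such patient.

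**Step 3: size of the morphine arm.** 150 × 1/2 = 75, which agrees with the figure in section 7. Section 16.3 gives 35 × 4 = 150, but 35 × 4 = 140; on that total the arm would be 70. This is a separate discrepancy and changes little here.

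**Step 4: how many patients.** The documents give no prevalence of recorded morphine allergy, so p below is an assumption. With n = 75:

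- expected number = n × p
- chance of at least one = 1 − (1 − p)^n

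| Assumed p | Expected among 75 | Chance of at least one |
|---|---|---|
| 0.1% | 75 × 0.001 = 0.075 | 1 − 0.999^75 = 7% |
| 0.5% | 75 × 0.005 = 0.375 | 1 − 0.995^75 = 31% |
| 1% | 75 × 0.01 = 0.75 | 1 − 0.99^75 = 53% |
| 2% | 75 × 0.02 = 1.5 | 1 − 0.98^75 = 78% |

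With n = 70 the expected numbers run from 0.07 to 1.4, and the chances are 7%, 30%, 51% and 76%.

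**Step 5: how many would become ineligible if both agents were covered.** Among 150 screened as otherwise eligible, 150 × 0.001 = 0.15 to 150 × 0.02 = 3.

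**The case against.** The best reply is that ordinary practice closes the gap. Every clinician on the study knows that any kit may contain morphine, since section 10 says so. An anaesthesiologist with an allergic patient need not know the allocation to see the problem. Section 10 also has the physician write a prescription according to the randomised arm and the pharmacy prepare the kit, so at least two professionals handle an arm-specific order. (That prescription conflicts with the blinding in 8.1 and needs its own reconciliation.) Section 9.5.2 allows withdrawal at the physician's discretion, and 8.1 contemplates unblinding when required without limiting it to events. Section 12.1 describes opioid management by the Acute Pain Service as standard care, so opioid allergy is presumably asked about anyway.

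Much of this stands, and it rules out some stronger readings:

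- *A reader might infer that she would be given morphine unknowingly.* The documents do not show that. Blinding conceals the allocation, not the possibility of morphine, and nothing indicates that routine checks would fail.
- *A reader might infer that the resulting non-treatment falls on the control arm alone and biases the comparison.* If staff are blinded, refusals on allergy grounds would fall on both arms. They concentrate in the morphine arm only if the allocation is already known. No effect on the primary analysis is shown.
- *A reader might cite section 4.1, where, on spinal morphine, "the risk for respiratory depression and other disturbing side-effects must be taken into account".* That is background on side effects of neuraxial adjuncts. It says nothing about allergy or eligibility.
- *A reader might take the 15.2 checklist as further evidence of a morphine-specific omission.* It omits clonidine allergy and galactose intolerance too. It is out of step with 7.2 in general.

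What the reply does not do is supply a written safeguard. None of these checks is required by the protocol, and those made at prescription, kit preparation or in the operating room come after randomisation.

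**Conclusion.** The gap is real and follows from the text alone: the eligibility rule screens for allergy to one of two randomised active intrathecal agents, so a patient with a known morphine allergy may be enrolled and has a 50% chance of allocation to morphine. Routine care may well intercept her. After randomisation, interception means either non-treatment or unblinding, and section 13.7 ends study medication once the blind is broken.

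The expected number is small: about 0.08 to 1.5 of 75 morphine-arm patients, under an assumed prevalence of 0.1% to 2% that has no source in the documents. The conclusion does not depend on that range. It concerns participant safety and clean randomisation; it does not show harm under blinding or a biased treatment comparison.

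**What to change.** Reconcile section 7.2 with the Study Summary, section 9.2.2 and section 10, so that the drug-allergy exclusion addresses both randomised intrathecal agents and their excipients and is applied before randomisation. The clinical wording, including what counts as a relevant history, is for the sponsor and investigators.

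Bring the 15.2 eligibility checklist into line with the whole of 7.2. That means adding the drug-allergy item for both agents and the galactose item, both of which are missing now.

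The cost is a protocol amendment changing one criterion, plus the checklist lines. At most a few patients become ineligible (0.15 to 3 of 150 under the same assumed prevalence). The sample size and the analysis plan need no change on this account.

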8 STUDY DESIGN/PROCEDURES

8.1 GENERAL DESIGN

This study is a randomized-controlled double-blind study. All consecutive female patients who come to the Shriners Hospital for Children – Canada, and who meet the Inclusion/exclusion criteria will be invited to participate in the study throughout the study's specified recruitment period to avoid selection bias.

Subjects will be expected to participate for 6 months. Subjects will be assessed for eligibility, consented and enrolled if they meet all criteria. They will undergo a baseline visit prior to surgery. CPM testing results will determine the subjects to be in one of two arms – 1) Sub-optimal endogenous inhibitory response or 2) Optimal endogenous inhibitory response. The subjects in each of these two groups will be randomized to either be treated with Clonidine arm or the placebo arm. Subjects will be followed in-hospital, and at 6 weeks and 6 months.

All clinicians and researchers involved in the recruitment, consent, data collection, experimental procedures and data analysis will remain blinded to study group allocation for the duration of the study. Blinding will be maintained until the end of statistical analysis, unless un-blinding is required. Although the study will be conducted at the Shriners Hospital for Children – Canada, including analysis of all specimens, the Pharmacy of the McGill University Health Centre will manage the randomization, blinding of medication/placebo as well as the distribution of the medication/placebo on the day of surgery and for 5 days post-operatively.

8.2 RECRUITMENT

Patients will be recruited from outpatient clinics at the Shriners Hospital for Children - Canada. Potential participants will be identified and informed of the study by their attending physician at the time of the examination and that presence of back pain is confirmed. If the subject expresses interest in learning more about the study, the physician and and/or a research assistant will then explain the study and answer any questions the subject or their family may have.

8.3 INFORMED CONSENT PROCESS

Informed consent will be obtained from the participants and/or their legally authorized representative by a member of the study staff authorized to consent for this study. Parents or legal guardians will consent for subjects 17 years and younger. As of the age of 18 years, the subjects may consent as adults. The process will include a thorough discussion, in a private area of the clinic, of all the elements outlined in the informed consent document, including but not limited to what is expected to happen during the study, risks and benefits of the planned therapy, and any possible alternatives. Subjects will be given adequate time to discuss with their family or physician and any questions they may have before deciding to participate in the study. Subjects who agree to participate in the study will be asked to sign the informed consent form. The informed consent form and the Shriner's "Documentation of Initial Informed Consent Discussion" will be scanned into the subject's hospital medical record and the originals will be filed, separately from the subject's study file, in the research coordinator's office at the Shriners Hospital. The subject and/or family will be given a copy of the signed consent form.

9 STUDY INFORMATION

9.1 BASELINE VISIT

The expected duration for the patient's participation in the research is 6 months and will consist of a baseline visit, In-hospital visit, 6 week post-op visit and a 6 month post-op visit.

At the baseline visit, the subject will be expected to complete the following:

- ✓ Pain intensity rating (self-reported) (Wong Baker Faces Pain Scale)

- ✓ Medical History Interview (Patient History Collection Form)
- ✓ Approximately 10 mL of blood will be drawn and blood pressure will be taken
- ✓ Quantitative Sensory Testing (QST = MDT/PPT/CPM tests)

The subject will be expected to fill out the following questionnaires:

- ✓ Pain numerical rating scale for children (Baseline - 4 questions)
- ✓ State-Trait Anxiety Inventory (STAI-C)
- ✓ Pain Catastrophizing Scale (PCS-C)
- ✓ Functional Disability Index (FDI)
- ✓ Revised Children Anxiety and Depression Scale (RCADS)
- ✓ Pittsburg Sleep Quality Index (PSQI)
- ✓ Neuropathic Pain Questionnaire (DN4)
- ✓ Tampa Scale for Kinesiophobia (TSK)
- ✓ Scoliosis Research Society (SRS-30)
- ✓ Adolescent Pediatric Pain Tool (APPT)

The visit should take approximately 1 hour

Once the subject's CPM results from the baseline visit have been assessed, the subject will be categorized into one of two arms: 1) Sub-optimal endogenous inhibitory response or 2) Optimal endogenous inhibitory response. The sub-optimal group will then be randomized to either Clonidine or the placebo, and the optimal group will be also randomized to either Clonidine or the placebo.

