Figure 3. Five empirically derived pain trajectories were identified in a subset of patients with Adolescent Idiopathic Scoliosis (n = 77) (Sieberg CB et al., 2013, PMID: 24290449). Illustrating that patients respond differently to painful surgical stimuli as well as to standardized analgesia regimen. Our hypothesis is that one can identify preoperatively (using QST and or biomarkers) how patient will respond to pain postoperatively.

A key mechanism of the central pain modulation is the endogenous analgesia system [31]. Efficacy of inhibitory mechanisms can be tested by using the response of conditioned pain modulation (CPM). It is a powerful analgesic mechanism illustrated when a painful stimulus is inhibited by a second painful stimulus delivered at a different body location [32]. In a previous study, we reported the CPM distribution in healthy subjects having no pain condition at the moment of the measurements (Figure 5). Approximately half (42%) of the healthy subjects had a pain reduction of 10% (minimal clinical change) or more [33].

Poor CPM, or lack of reduction in pain during the presence of the conditioning stimuli was reported in patients with various chronic pain disorders [34-36]. The risk of developing chronic pain following surgical procedure is related to lower efficacy of CPM in humans [37,19]. Although used to assess perioperative efficacy of endogenous inhibition in adults, the use of CPM during the perioperative period surrounding a surgery in pediatric patients has not yet been evaluated.

Considering that the modulatory effects of the endogenous inhibition are largely mediated by descending serotonergic and noradrenergic pathways [38,39], we further studied

catecholamines as possible biomarkers of pain. Multivariate analyses of perioperative catecholamines levels revealed preoperative plasmatic concentrations of norepinephrine (NE) and normetanephrine (NME) and the cerebrospinal fluid (CSF) concentration of NE were significantly correlated with the presence of pain six weeks after surgery ($r = 0.50, 0.49$ and 0.50 respectively, $p < 0.002$), (Figure 6) [30]. These results support the evidence for a potential role of the endogenous inhibitory mechanism and catecholamine levels in predicting postoperative pain intensity and provide clues as to a mechanism-based pre-analgesic approach to perioperative pain management.

Catecholamines	Pain	Plasma (n=50)	CSF (n=38)
NE	Preoperative	$r = .05, p = 0.70$	$r = .11, p = 0.51$

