16.3 SAMPLE SIZE DETERMINATION AND POWER / ACCRUAL RATE

The sample size was calculated for the primary outcome (average pain intensity over the past 7 days six months after surgery). Assuming that a 2-point change on the 0–10 pain intensity scale constitutes a clinically meaningful difference [74,76], a standard deviation of 2.0 units, a study design with 3 repeated measurements having a compound symmetry covariance matrix, a power of 90%, a two-sided alpha level of 0.05 and a conservative autocorrelation coefficient (rho) of one,

a minimum of 22 patients per comparison group is required. To prevent reduced power because of patient loss to follow-up and to minimize confounding effects, 35 patients per group will be enrolled (35 x 4 groups = 150 patients in total).

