16.5 STRATIFICATION FACTORS

The chosen study design (Figure 7) will test different hypotheses and comparisons between the following groups:

- 1) Placebo group of patients with sub-optimal endogenous inhibitory response vs placebo group of patients with optimal response to test whether patients with inadequate endogenous inhibitory response before surgery are more at risk to develop chronic postsurgical pain (CPSP) than patients with optimal response.
- 2) Clonidine vs placebo group of patients with sub-optimal endogenous inhibitory response to test whether a pharmacological intervention focused on restoring the normal function of the descending inhibitory system reduces the incidence of acute and chronic pain after surgery.

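### Baseline CPM is planned as a predictor of pain only in two classes; entering the graded score in the planned mixed model would use more of the information already collected

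*Combined protocol and SAP*

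**What the plan says.** Section 6 opens: "The primary objective of this study is to evaluate if pre-operative QST can identify if patients will have high pain intensity", both peri-operatively and at six months. Sections 8.1, 9.1 and 10 turn the baseline result into an optimal or sub-optimal response; in Section 9.1, "the subject will be categorized into one of two arms". Patients are then randomised 1:1 to clonidine or placebo within each class.

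The comparison that serves the primary objective is the first in Section 16.5: "Placebo group of patients with sub-optimal endogenous inhibitory response vs placebo group of patients with optimal response". Section 16.4 applies linear mixed models for repeated measures to each comparison. The named covariates are age, functional outcome score, STAI and PCS; a CPM value is not among them. Section 16.4 also has a secondary repeated-measures analysis concerned with change over time in QST, but does not say that baseline CPM predicts pain in it.

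The underlying measurement is graded. Pain is rated on the CoVAS during a two-minute thermode test before and after the cold bath (Sections 11.2.4.2 and 11.2.4.4). The readable text does not say how these ratings become a CPM score, or where sub-optimal begins. The only related figure is background in Section 4: in an earlier study, 42% "of the healthy subjects had a pain reduction of 10% (minimal clinical change) or more". It is not adopted as this trial's rule.

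**The concern.** A cut is needed to form randomisation strata and to define the patients in comparison 2 (clonidine versus placebo among sub-optimal responders). Comparison 1 is different. It compares placebo patients with each other by a characteristic they had before surgery, so it is prognostic and the randomisation does not require a cut in its analysis.

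Using classes there treats patients just either side of the threshold as different and all patients on one side as alike. If pain changes gradually with CPM, precision is lost and the answer to the primary objective is tied to one threshold. A true association of moderate size could be missed although the data to detect it had been collected.

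**Working it through.** **1. The plan's own sample size.** Inputs from Section 16.3: "Assuming that a 2-point change on the" 0–10 scale is clinically meaningful; "a standard deviation of 2.0 units"; "a two-sided alpha level of 0.05"; 90% power; "a study design with 3 repeated measurements having a compound symmetry covariance matrix"; and rho of one. With k = 3 measurements the repeated-measures factor is (1 + (k − 1)rho)/k = (1 + 2)/3 = 1, so this is an ordinary two-sample comparison:

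n = 2 × [(1.960 + 1.282) × 2/2]² = 21.01, rounded up to 22 per group. The stated 22 reproduces (a t-based calculation gives 23).

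**2. Class-contrast power at the planned enrolment.** With 35 per group, the standardised difference over its standard error is (2/2)/√(2/35) = 4.18. Power is Φ(4.18 − 1.96) = 98.7%, or 98.5% with the t distribution. With 22 per group it is about 90% to 91%.

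**3. Information kept by two classes.** Assume a normal CPM score with a linear effect on pain, and let p be the share in one class. The efficiency relative to the continuous score is φ(z_p)²/[p(1 − p)].

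| Split | φ(z_p)² | p(1 − p) | Efficiency | Loss |
|---|---|---|---|---|
| 50/50 | 0.1592 | 0.2500 | 0.637 | 36.3% |
| 42/58 | 0.1528 | 0.2436 | 0.627 | 37.3% |
| 30/70 | 0.1209 | 0.2100 | 0.576 | 42.4% |
| 20/80 | 0.0784 | 0.1600 | 0.490 | 51.0% |

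The 42/58 split borrows the healthy-subject figure from Section 4. Equal groups of 35 correspond to 50/50. Simulated losses at 42/58 for other shapes are about 27% (uniform), 46% (exponential, upper 42%) and 50% (t with 4 df). At 42/58 under normality, the 35 + 35 = 70 placebo patients carry the information of 70 × 0.627 ≈ 44 analysed on the continuous score.

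**4. Illustrative power.** The documents give no correlation between CPM and post-operative pain in this population, so r is assumed. Power by Fisher z is Φ(atanh(r)√(n − 3) − 1.96). In classes at 42/58, r shrinks by √0.627 = 0.792.

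For r = 0.30 and n = 70:
- Continuous: 0.3095 × √67 = 2.53, power 72%.
- Classes: r = 0.30 × 0.792 = 0.238; 0.2422 × √67 = 1.98, power 51%.

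| Assumed r (n = 70) | Continuous | Two classes |
|---|---|---|
| 0.30 | 72% | 51% |
| 0.35 | 85% | 64% |
| 0.40 | 93% | 77% |

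An even split barely changes the class figure (51.5% at r = 0.30). At r = 0.30, n = 75 gives 75% against 54%, and n = 44 (two groups of the stated minimum) gives 51% against 34%.

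**5. How these effects compare with the planned one.** At 42/58 and within-class SD 2, r = 0.30 implies a class difference of 2 × 0.238/[√(1 − 0.238²) × √0.2436] ≈ 1.0 point, half the design difference. Conversely, a 2-point difference with SD 2 at 50/50 implies a class correlation of 1/√5 = 0.45, and so about 0.45/0.798 = 0.56 with the continuous score. The largest correlation between a pre-operative measure and follow-up pain in Section 4 is 0.50, for pre-operative pain and for catecholamines, not for CPM.

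**The case against.** The strongest reply is that the trial is sized for a 2-point class difference, and step 2 shows ample power for it. That stands. A reader might infer that the primary objective is underpowered; on the protocol's own assumptions it is not. The 72% against 51% is an illustration at about half the planned effect, from a simple correlation rather than the covariate-adjusted repeated-measures model. Still, the design effect implies a correlation above any pre-operative one in the pilot data, and Section 4 says CPM has not yet been evaluated perioperatively in pediatric patients, so smaller effects deserve consideration.

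A reader might also take 37% as what this plan loses. The documents do not support that: no split or distribution is given for these patients, and the 42% comes from healthy subjects without pain, whereas Section 8.2 describes recruitment with back pain confirmed. Only a conditional range is defensible.

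Third, the central hypothesis is about identifying patients with poor inhibition, which is a classification question; if risk really steps at a threshold, classes can be the more efficient analysis. This is a reason to check linearity and to keep the class contrast, not to omit the graded score.

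Finally, it would go too far to say that QST is never analysed in graded form, or that no rule exists anywhere. Section 16.4 has the secondary analysis of change over time. It also mentions three comparison schemes where Section 16.5 lists two and points to Figure 7, which, like the study schema, could not be read here.

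**Conclusion.** The point holds for the prognostic question, within the readable text: baseline CPM predicts pain only as two classes, although a graded measurement is collected and the design does not need the cut for that analysis. Under a normal score and a linear effect the loss is about 36% to 37% for splits between 50/50 and 42/58, rising to 51% at 20/80; at 42/58 it runs from about 27% to 50% across the other shapes tried. It does not undermine power at the planned 2-point difference. It matters if the true association is weaker, at correlations of roughly 0.30 to 0.40. Stratifying the randomisation by class is not at fault. The unstated cut-off, taken alone, is missing detail rather than an error of method, but it must be supplied for either analysis to be reproducible.

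**What to change.** Keep the two classes for stratified randomisation and for comparison 2. In Section 16.4, for the prognostic question in placebo patients, enter continuous baseline CPM as the predictor in the mixed model already planned. Retain both the six-week and the six-month pain scores: a six-month-only model would drop part of the primary endpoint in Section 16.1 and the repeated-measures structure. Check linearity, for example with one spline term, and report the two-class contrast alongside.

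Two things come first. The thermode rating before the bath is anchored 0 to 20 (Section 11.2.4.2) and the one after the bath 0 to 10 (Section 11.2.4.4). These passages must be reconciled, because no change score can be computed reliably across them. The plan must then state how the CPM score is calculated from the ratings and how the class follows from it, before any unblinding.

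The cost is one extra model, a linearity assumption to check, and a short addition to Sections 9.1 and 16.4. No new visits, measurements or patients are needed. As Section 16.3 is written for a group comparison, a sentence on the precision expected from the continuous model should be added.
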